12.3. Appendix 3: Study Phases and Treatment Emergent Adverse Events

12.3.1. Study Phases

Assessments and events will be classified according to the time of occurrence relative to study treatment start date.

Study Phase	Definition
Pre-Treatment	Date ≤ Study Treatment Start Date/Time
Treatment Emergent	Date > Study Treatment Start Date/Time

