5.1. Inclusion Criteria

Participants are eligible to be included in the study only if all of the following criteria apply:

Age

1. Participants must be 18 to 65 years of age inclusive, at the time of signing the informed consent.

Type of Participant and Disease Characteristics

2. Participants who are overtly healthy as determined by medical evaluation including medical history, physical examination, laboratory tests and 12-lead ECGs
3. A participant with a clinical abnormality or laboratory parameter(s) outside the reference range for the healthy population being studied that is not specifically listed in the inclusion or exclusion criteria may be included if the investigator and GSK Medical Monitor agree and document that the finding is unlikely to introduce additional risk factors and will not interfere with the study procedures or interpretation.

Weight

4. Body weight ≥ 45 kg and body mass index (BMI) within the range 18.5-29.9 kg/m² (inclusive).

Sex

5. Male

Informed Consent

6. Capable of giving signed informed consent which includes compliance with the requirements and restrictions listed in the ICF and in this protocol.

Geographical Ancestry

7. Japanese ancestry, defined as having been born in Japan, being descendants of four ethnic Japanese grandparents and two ethnic Japanese parents, holding a Japanese passport or identity papers, and being able to speak Japanese. Participants should have lived outside Japan for less than 10 years at the time of screening.

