5.2. Exclusion Criteria

Participants are excluded from the study if any of the following criteria apply:

Medical Conditions

1. Sensitivity to any of the study treatments or components there of (including humanised monoclonal antibodies) or history of severe post treatment hypersensitivity reactions including erythema multiforme major, linear immunoglobulin A (IgA) dermatosis, toxic epidermal necrolysis and exfoliative dermatitis.
2. Any other history of significant allergy that in the opinion of the investigator contraindicates their participation in this study.
3. An active infection or a history of serious infections as follows:
 - a. Use of antimicrobials (antibacterials, antivirals, antifungals or antiparasitic agents) for an infection within 30 days prior to Day 1. Topical treatments may be allowed at the Investigator's discretion (in consultation with the Medical Monitor).
 - b. A history of opportunistic or recurrent infections, as determined by the investigator.
 - c. Currently active or unresolved infection. Participants with 'trivial' infections such as tinea pedis may be eligible at the discretion of the investigator.
 - d. Symptomatic herpes zoster within 3 months prior to screening.
 - e. History of TB (active or latent) irrespective of treatment status.
 - f. A positive diagnostic TB test at screening (defined as a positive QuantiFERON test).

NOTE: In cases where the QuantiFERON test is indeterminate, the participant may have the test repeated once and will be eligible if the second test is negative.

4. Any planned major surgical procedure during the study.
5. A history of haematological disease, for example (but not limited to): significant anaemia, platelet disorders including drug-induced thrombocytopenia or primary immune thrombocytopenia and coagulation disorders including von Willebrand's disease.
6. A history of carcinoma in situ and malignant disease, with the exception of adequately treated non-metastatic basal or squamous cell cancer of the skin that has been fully treated and shows no evidence of recurrence after 3 years.

7. QTc >450 msec at screening.

NOTE: The QTc is the QT interval corrected for heart rate according to Fridericia's formula (QTcF), or another method, machine-read or manually over-read. The same correction is to be used throughout the study.

Prior/Concomitant Therapy

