9.4.2. Primary Endpoint(s)

Analysis	Details
Endpoints	
 • Number of participants reporting AEs and SAEs • Number of participants with vital signs (blood pressure, heart rate, body temperature) reaching a threshold of potential clinical importance • Number of participants with treatment emergent abnormal ECG findings. • Number of participants with CTCAE grade 1 or higher safety laboratory results (clinical chemistry, haematology values where CTCAE grading applies). • Number of participants with treatment emergent abnormal urinalysis findings.
Analysis	
 • For count data, the number and percentage of participants will be presented. • In addition, where continuous data is available, descriptive statistics (i.e. n, arithmetic mean, standard deviation, minimum, median, and maximum) of both raw and change from baseline data will be also presented. • CTCAE criteria (version 5) will be used to categorise laboratory safety data.

 • Statistical Analysis (Modelled) 	
 • No statistical modelling is planned.

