12.3.2. Treatment Emergent Flag for Adverse Events

Adverse Events will be flagged as Treatment Emergent as described in the table in Section [12.3.1](#), where the AE Start Date/Time will be considered.

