3.16.	Safety	SAFE_T4	Summary of Worst Case Urinalysis Results Post-Baseline Relative to Baseline	Tests to include: Urine blood, Urine Glucose (dipstick), Urine Ketones (dipstick), Urine Microscopy – Bacteria, Urine Microscopy - Red Blood Cells, Urine Microscopy - White Blood Cells, Urine Protein (dipstick), Urine Specific Gravity	SAC
ECG					
3.17.	Safety	EG1	Summary of ECG Findings		SAC
3.18.	Safety	EG2	Summary of ECG Values	Footnote: Average used for triplicate ECG measurements	SAC
3.19.	Safety	EG2	Summary of Change from Baseline in ECG Values	Footnote: Average used for triplicate ECG measurements	SAC
Vital Signs					
3.20.	Safety	VS1	Summary of Change from Baseline in Vital Signs		SAC
3.21.	Safety	VS7	Summary of Worst Case Vital Signs Results Relative to Potential Clinical Importance (PCI) Criteria Post-Baseline Relative to Baseline		SAC

CONFIDENTIAL

208564

Safety: Tables					
No.	Population	IDSL / Example Shell	Title	Programming Notes	Deliverable [Priority]
3.22.	Safety	SAFE_T5	Summary of Worst Case Vital Sign Results Relative to Change from Baseline Potential Clinical Importance (PCI) Criteria		SAC
Immunogenicity					
3.23.	Safety	IMM1	Occurrence of Anti-Drug Antibodies	Add footnote: Note: The denominator for confirmed positive is the total number of subjects at that visit who have immunogenicity data available.	SAC

CONFIDENTIAL

208564

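### The primary ECG endpoint has no baseline-referenced derivation: the SAP defines treatment emergent by timing alone, and its only table of ECG findings states no comparison with baseline

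*SAP*

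**What the plan says.** Protocol 3 and 9.4.2 and SAP 2.2 list as a primary endpoint the "Number of participants with treatment emergent abnormal ECG findings".

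SAP 12.3.1 sets the phase rule: "Assessments and events will be classified according to the time of occurrence relative to study treatment start date". Its treatment-emergent row reads "Date > Study Treatment Start Date/Time". SAP 12.3.2 then puts the rule to use for one data type: "Adverse Events will be flagged as Treatment Emergent as described in the table in Section" 12.3.1, using the start of the adverse event. ECG findings have no flag rule of their own.

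In SAP 12.9.5, Table 3.17 is "Summary of ECG Findings", on standard shell EG1, with no programming note. Table 3.19 is "Summary of Change from Baseline in ECG Values", and Figures 3.4 and 3.5 show change in QTcF. SAP 4.2 defines a baseline for every endpoint as the last non-missing value before dosing, unscheduled visits included.

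On entry, the only ECG-specific exclusion in Protocol 5.2 is "QTc >450 msec at screening". Under criterion 3 of Protocol 5.1, a participant with another abnormality "may be included if the investigator and GSK Medical Monitor agree and document that the finding is unlikely to introduce additional risk factors", among other conditions.

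**The concern.** A timing rule works for an adverse event because the event has an onset. An ECG tracing has only a recording time, and every post-dose tracing falls after dosing. Applied literally, the rule labels an unchanged pre-dose abnormality as treatment emergent at each post-dose ECG. The endpoint would then report the post-dose prevalence of abnormal ECGs instead of abnormalities that appeared after dosing.

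The rule treats both arms alike, so it adds non-specific counts and does not systematically favour one arm. With seven active and three placebo participants, though, a chance imbalance in long-standing ECG variants could look like a drug effect or mask one.

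**Working it through.** **Step 1. Compare two primary endpoints that use the same phrase.**

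| | Urinalysis | ECG findings |
|---|---|---|
| Endpoint wording | treatment emergent abnormal | treatment emergent abnormal |
| SAP table | 3.16 | 3.17 |
| Title refers to baseline | yes | no |
| Shell | SAFE_T4, shown in SAP 12.10; separates no change or decrease from any increase | EG1, not shown |
| Participant-level post-baseline count stated | yes (worst case) | no |

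Tables 3.9, 3.12, 3.13 and 3.21 (chemistry, haematology, vital signs) also state a comparison with baseline in their titles.

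**Step 2. Check the other ECG displays.** Table 3.19 and Figures 3.4 and 3.5 do use baseline, but for interval values and QTcF change, not for abnormal findings. The title of Listing 25 (abnormal ECG findings) mentions neither baseline nor treatment emergence.

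**Step 3. Reproduce the protocol's scale.** Protocol 9.2, Table 2, uses a Beta(1,1) prior. The equal-tailed 95% limits for x events in n participants are the 2.5% and 97.5% points of Beta(1 + x, 1 + n − x). All six rows of Table 2 reproduce. Those for n = 7:

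| Events | Protocol Table 2 | Recomputed |
|---|---|---|
| 0/7 | 0.3% to 37% | 0.32% to 36.94% |
| 1/7 | 3.2% to 53% | 3.19% to 52.65% |
| 2/7 | 8.5% to 65% | 8.52% to 65.09% |

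For 0/7 the upper limit has a closed form: 1 − 0.025^(1/8) = 0.369.

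**Step 4. Effect of one persistent abnormality.** Suppose no new ECG finding occurs.

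- Active: a baseline-referenced count gives 0/7 (upper limit 36.9%). A timing-only count gives 1/7 = 14.3% (upper limit 52.7%). With two such participants it gives 2/7 (65.1%).
- Placebo: the count moves from 0/3 to 1/3 = 33.3%.

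**Step 5. How likely is it?** The documents give no prevalence of abnormal ECG findings at baseline, so p below is an assumption. The chance of at least one affected participant among n, taken as independent, is 1 − (1 − p)^n.

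| Assumed p | n = 7 (active) | n = 3 (placebo) | n = 10 (all) |
|---|---|---|---|
| 2% | 13% | 6% | 18% |
| 5% | 30% | 14% | 40% |
| 10% | 52% | 27% | 65% |
| 20% | 79% | 49% | 89% |
| 30% | 92% | 66% | 97% |

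For example, 1 − 0.95^10 = 0.40. These are chances that an affected participant is enrolled. A miscount also requires that the abnormality persists after dosing and that the table ignores baseline.

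**The case against.** The strongest reply is that nothing shows a miscount will happen. The appendix holding the rule is headed for adverse events, and 12.3.2 applies the flag to adverse events only. Table 3.17 is not labelled treatment emergent. SAP 7.3 defers ECG analyses to company standards, and EG1 may display baseline. The urinalysis table suggests that the sponsor already reads the phrase as relative to baseline. All of this stands against the stronger claim a reader might infer, that pre-existing abnormalities are going to be counted as drug effects. It does not supply the missing derivation. If 12.3.1 does not govern ECGs, the endpoint has no definition of treatment emergent at all. A visit-by-visit shell that happens to include baseline would still not give a participant count of new findings.

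A reader might also infer that the SAP makes no ECG comparison with baseline. That is wrong for interval values and QTcF change, as step 2 shows.

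Nor do the entry criteria imply that many affected participants will enrol. Criterion 2 of Protocol 5.1 requires overt health on an evaluation that includes 12-lead ECGs, and criterion 3 requires documented agreement that the finding will not interfere with interpretation. This argues for the lower rows of the last table, but excludes no one with an accepted ECG variant.

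Finally, the study is descriptive and small, so a reader could work through the listings case by case. That limits the harm, but the reported primary count still needs a rule.

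**Conclusion.** The concern holds as a missing derivation for a primary endpoint, made worse by a general timing rule that gives the wrong answer if applied literally to ECG findings. The documents do not establish that pre-existing abnormalities will be counted; they leave it possible, in both arms.

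One persistent abnormality shifts the active result by one in seven and raises the upper credible limit from 37% to 53%, or shifts placebo by one in three. These figures assume the planned 7:3 allocation, no genuinely new findings, and a count that follows the timing rule. No single probability can be given, because it rests on an assumed prevalence: from 18% at p = 2% to 89% at p = 20% for at least one affected participant in ten. The correction is cheap and worth making.

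**What to change.** 1. In SAP 12.3, add that an abnormal ECG finding is treatment emergent only if it is new or worsened relative to the SAP 4.2 baseline. Refer to that definition and do not fix the comparator at Day 1 pre-dose, so that a missing Day 1 ECG does not leave a participant without one.
2. Make Table 3.17 baseline-referenced in title and content, in the style of Table 3.16, and name it as the display for this primary endpoint. Include one any-time-post-baseline participant count per arm that covers unscheduled ECGs. This row is needed because SAP 12.2 keeps only the visit closest to each analysis timepoint, so an unscheduled abnormal ECG could drop out of a by-visit summary.
3. If the PR, QRS and QTc limits in SAP 12.7.3 are tabulated, do so in a separate supportive display. Folding them into this count would change the endpoint, which concerns abnormal findings.

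The cost is a sentence in the SAP and a revised table shell. Baseline ECGs are already collected in triplicate, so no new data are needed.

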12.3.1.1. Study Phases for Concomitant Medication

Study Phase	Definition
Prior	If medication end date is not missing and is prior to study treatment
Concomitant	Any medication that is not a prior

NOTES:

- Please refer to [Appendix 6](#): Reporting Standards for Missing Data for handling of missing and partial dates for concomitant medication. Use the rules in this table if concomitant medication date is completely missing.

12.3.2. Treatment Emergent Flag for Adverse Events

Adverse Events will be flagged as Treatment Emergent as described in the table in Section [12.3.1](#), where the AE Start Date/Time will be considered.

12.4. Appendix 4: Data Display Standards & Handling Conventions

12.4.1. Reporting Process

Software			

 The currently supported versions of SAS software will be used. 			
Reporting Area			
HARP Server	: \\uk1salx00175.corpnet2.com		
HARP Compound	Reporting effort (RE) name in RAP	Type	HARP folder / RE name
	Unplanned IA	Interim analysis	internal_01, internal_02
	SAC	Pre-programming/ dry run	data_look_01, data_look_02
	SAC	Final	final_01
Analysis Datasets			

 Analysis datasets will be created according to Integrated Data Standards Library (IDSL) GSK A&R dataset standards. 			
Generation of RTF Files			

 RTF files will be generated for SAC 			

12.4.2. Reporting Standards

General	

 The current GSK Integrated Data Standards Library (IDSL) will be applied for reporting, unless otherwise stated (IDSL Standards Location: https://spope.gsk.com/sites/IDSLLibrary/SitePages/Home.aspx): 
 4.03 to 4.23: General Principles 5.01 to 5.08: Principles Related to Data Listings 6.01 to 6.11: Principles Related to Summary Tables 7.01 to 7.13: Principles Related to Graphics Do not include subject level listings in the main body of the GSK Clinical Study Report. All subject level listings should be located in the modular appendices as ICH or non-ICH listings 	
Formats	

 All data will be reported according to the actual treatment the participant received. GSK IDSL Statistical Principles (5.03 & 6.06.3) for decimal places (DP's) will be adopted for reporting of data based on the raw data collected, unless otherwise stated. Numeric data will be reported at the precision collected on the eCRF. The reported precision from non eCRF sources will follow the IDSL statistical principles but may be adjusted to a clinically interpretable number of DP's. Dates will be reported in the format DDMMCCYY e.g. 01Jan2020 unless otherwise stated. 	
Planned and Actual Time	

 Reporting for tables, figures and formal statistical analyses: 
 Planned time relative to dosing will be used in figures, summaries, statistical analyses and calculation of any derived parameters, unless otherwise stated. 	

CONFIDENTIAL

208564

 The impact of any major deviation from the planned assessment times and/or scheduled visit days on the analyses and interpretation of the results will be assessed as appropriate. Reporting for Data Listings: 
 Planned and actual time relative to study drug dosing will be shown in listings (Refer to IDSL Statistical Principle 5.05.1). Unscheduled or unplanned readings will be presented within the subject's listings. 	
Unscheduled Visits	

 Unscheduled visits will be included in summary tables and figures. Assessment windows for the unscheduled and early withdrawal assessments are specified in Appendix 2: Assessment Windows. All unscheduled visits will be included in listings. 	
Descriptive Summary Statistics	
Continuous Data	Refer to IDSL Statistical Principle 6.06.1
Categorical Data	
N, n, frequency, %
 
N = the number of participants from the relevant analysis population for the group or subgroup.
 
n = the number of participants counted for the summary statistic.

Graphical Displays	

 Refer to IDSL Statistical Principles 7.01 to 7.13. 	

12.4.3. Reporting Standards for Pharmacokinetic

Pharmacokinetic Concentration Data	
Descriptive Summary Statistics, Graphical Displays and Listings	
Refer to IDSL PK Display Standards.
 
Refer to IDSL Statistical Principle 6.06.1.
 
Note: Concentration values will be imputed as per GUI_51487 for descriptive summary statistics/analysis and summarized graphical displays only.

PC Windows Non-Linear (WNL) File for GSK2330811	
PC WNL file (CSV format) for the non compartmental analysis by Clinical Pharmacology Modelling and Simulation function will be created according to GUI_51487.
 
Note: Concentration values will be imputed as per GUI_51487.
 
Note: GSK2330811 concentration values will be imputed as per GUI_51487.

Pharmacokinetic Parameter Derivation	
PK Parameter to be Derived by Programmer	None
Pharmacokinetic Parameter Data	
Is NQ impacted PK Parameters Rule Being Followed	
Yes, refer to SOP_314000.. If one or more non-quantifiable (NQ) values occur in a profile before the first measurable concentration, they will be assigned a value of zero concentration. For linear plots, zero concentration value(s) before the first measurable concentration will be included in the plot. For log-linear plots, zero concentration value(s) before the first measurable concentration will be assigned a missing value. If a single NQ value occurs between measurable concentrations in a profile, the NQ should generally be omitted (set to missing) in the derivation of pharmacokinetic parameters, statistical analysis, and the individual subject plots.
 
If two or more NQ values occur in succession between measurable concentrations, the profile will be deemed to have terminated at the last measurable concentration prior to these NQs. For the purpose of individual subject plots, these NQs will be set to 0, and the subsequent measurable concentrations will be retained. For the

CONFIDENTIAL

208564

	
derivation of pharmacokinetic parameters, these NQs and any subsequent measurable concentrations will be omitted (set to missing).
 
NQs which occur after the last measurable concentration will be omitted (set to missing) in the derivation of pharmacokinetic parameters and from the individual subject plots. In some circumstances, there may be a pharmacokinetic rationale for fluctuation resulting in non-measurable concentrations in the middle of the concentration-time profile (e.g., entero-hepatic recycling, erratic absorption from transdermal/inhaled formulations). In these cases, the NQ values could be set to missing or to some other values (e.g., $\frac{1}{2}$ LLQ) and subsequent valid concentrations may be retained. A reference line indicating LLQ will be included in plots.
 
For the calculation of mean or median pharmacokinetic profiles. When estimating the mean or median value for the concentration at a given time point (i.e., descriptive mean or median curve), the following guidelines should be considered:
 
All NQ values will be set to zero except when an individual NQ falls between two quantifiable values, in which case it will be omitted from the calculation of mean or median profiles. Measurable concentrations which follow more than one consecutive mid-profile NQ will be omitted (set to missing). The mean/median value at a time-point where one or more samples have NQ values will be reported (in tabular or graphical fashion) even if the mean/median value is below the LLQ of the assay. For linear plots, zero concentration value(s) will be included in the plot. For log-linear plots, zero concentration value(s) will be assigned a missing value.
 
Zero mean or median values will be included in summary tables. In certain cases, the NQ values could be set to missing or to some other values (e.g., $\frac{1}{2}$ LLQ) with proper scientific justification(s). A reference line indicating LLQ will be included in plots.
 
It should be noted that a high proportion of NQ values may affect the standard deviation (SD); if more than 30% of values are imputed, then SD will not be displayed. Any table of summary statistics for concentration-time data will report N (number of subjects in the analysis population), n (number of subjects with non-missing values) and number imputed (number of subjects with imputed values (i.e., NQ assigned zero concentration)).
 
BQL (Below the Quantification Limit) may be displayed in listings by legacy systems instead of NQ; these abbreviations are interchangeable and mean that a sample has been received, analysed and a concentration below the LLQ of the assay found. Scientific judgement and prior knowledge should always be used in applying these guidelines.

Descriptive Summary Statistics, Graphical Displays and Listings	Refer to IDSL PK Display Standards. Refer to GUI_51487

CONFIDENTIAL

208564

12.4.4. Reporting Standards for Target Engagement

Total OSM Concentration Data	
Descriptive Summary Statistics, Graphical Displays and Listings	
Refer to IDSL PK Display Standards.
 
Refer to IDSL Statistical Principle 6.06.1.
 
Note: Concentration values will be imputed as per GUI_51487 for descriptive summary statistics/analysis and summarized graphical displays only.

PC Windows Non-Linear (WNL) File for Total OSM	
PC WNL file (CSV format) for the non compartmental analysis by Clinical Pharmacology Modelling and Simulation function will be created according to GUI_51487.
 
Note: Total OSM concentration values will be imputed as per GUI_51487.

Total OSM Parameter Derivation	
Total OSM Parameter to be Derived by Programmer	None
Total OSM Parameter Data	
Is NQ impacted Total OSM Parameters Rule Being Followed	
Yes, refer to SOP_314000. If one or more non-quantifiable (NQ) values occur in a profile before the first measurable concentration, they will be assigned a value of zero concentration. For linear plots, zero concentration value(s) before the first measurable concentration will be included in the plot. For log-linear plots, zero concentration value(s) before the first measurable concentration will be assigned a missing value. If a single NQ value occurs between measurable concentrations in a profile, the NQ should generally be omitted (set to missing) in the derivation of total OSM parameters, statistical analysis, and the individual subject plots.
 
If two or more NQ values occur in succession between measurable concentrations, the profile will be deemed to have terminated at the last measurable concentration prior to these NQs. For the purpose of individual subject plots, these NQs will be set to 0, and the subsequent measurable concentrations will be retained. For the derivation of total OSM parameters, these NQs and any subsequent measurable concentrations will be omitted (set to missing).
 
NQs which occur after the last measurable concentration will be omitted (set to missing) in the derivation of pharmacokinetic parameters and from the individual subject plots.
 
For the calculation of mean or median total OSM profiles. When estimating the mean or median value for the concentration at a given time point (i.e., descriptive mean or median curve), the following guidelines should be considered:
 
All NQ values will be set to zero except when an individual NQ falls between two quantifiable values, in which case it will be omitted from the calculation of mean or median profiles. Measurable concentrations which follow more than one consecutive mid-profile NQ will be omitted (set to missing). The mean/median value at a time-point where one or more samples have NQ values will be reported (in tabular or graphical fashion) even if the mean/median value is below the LLQ of the assay. For linear plots, zero concentration value(s) will be included in the plot. For log-linear plots, zero concentration value(s) will be assigned a missing value.
 
Zero mean or median values will be included in summary tables. In certain cases, the NQ values could be set to missing or to some other values (e.g., $\frac{1}{2}$ LLQ) with proper scientific justification(s). A reference line indicating LLQ will be included in plots.
 
It should be noted that a high proportion of NQ values may affect the standard deviation (SD); if more than 30% of values are imputed, then SD will not be displayed.


CONFIDENTIAL

208564

	
Any table of summary statistics for concentration-time data will report N (number of subjects in the analysis population), n (number of subjects with non-missing values) and number imputed (number of subjects with imputed values (i.e., NQ assigned zero concentration)).
 
BQL (Below the Quantification Limit) may be displayed in listings by legacy systems instead of NQ; these abbreviations are interchangeable and mean that a sample has been received, analysed and a concentration below the LLQ of the assay found. Scientific judgement and prior knowledge should always be used in applying these guidelines.

Descriptive Summary Statistics, Graphical Displays and Listings	
Refer to IDSL PK Display Standards.
 
Refer to GUI_51487

